**Table 2: CUDC-907 Dose Adjustments for Hematologic and Non-Hematologic Toxicities (Continued)**

Toxicity	Management		
Hyperglycemia	Grade 1/2 or Grade 3 (> 250 – 500 mg/dL) asymptomatic No change in dose 	Grade 3 (> 250 – 500 mg/dL) symptomatic or Grade 4 (> 500 mg/dL) Hold treatment until glucose < 250 mg/dL and asymptomatic; Reduce dose to the next lower dose level (as applicable per Table 1 ).	≥ Grade 3 hyperglycemia not improving despite appropriate treatment for 1 week or symptomatic Grade 4 hyperglycemia (> 500 mg/dL) Hold treatment until glucose < 250 mg/dL and asymptomatic; Reduce dose to the next lower dose level (as applicable per Table 1 ) upon return to ≤ Grade 1 or baseline.

Recurrence of Grade 3 or 4 hyperglycemia will be cause for a second dose modification.  If the starting dose does not permit dose modification, then study drug will be discontinued.  Recurrence of Grade 3 or 4 hyperglycemia that does not recover to ≤ Grade 1 or baseline within 3 weeks after second modification (as applicable) will be grounds for discontinuation of study drug.
			

AEs = adverse events; ANC = absolute neutrophil count

 Transient Grade 1 or 2 hyperglycemia should be monitored per Investigator discretion and medical guidelines.

 An exception for ongoing treatment may be made in the case of Investigator-determined clinical benefit with approval from the Medical Monitor.

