## 8. STUDY DESIGN

### 8.1. Overall Study Design

This is a Phase 2, open-label, multicenter trial designed to evaluate the efficacy and safety of CUDC-907 in subjects 18 years and older with RR MYC-altered DLBCL.

[Figure 1](#) depicts the study design. Patients with RR DLBCL will be eligible for treatment with CUDC-907 as long as they have tumor tissue available that can be tested for MYC-altered disease. This is defined as *MYC* translocation by FISH, or *MYC* expression in  $\geq 40\%$  of tumor cells by IHC staining, and/or *MYC* gene copy number gain by FISH based on central testing of one of the following:

- Fresh tumor tissue obtained from biopsy accessible lesions with low estimated risk for serious complications (less than 2%), or
- Archived tumor tissue (most recent available)

Subjects will be required to submit archival tumor samples (most recent available) or fresh tumor samples for central FISH and IHC testing. Subjects whose tumors have been previously characterized as MYC-altered are strongly encouraged to enter the study. For subjects who enter the study with unconfirmed MYC-altered disease, fresh tumor samples are preferred.

All eligible subjects will receive the following treatment:

- CUDC-907 60 mg ( $2 \times 30$  mg capsules) orally (PO) for 5 days on/2 days off (5/2) (21-day cycles).

Based on central testing and review, subjects will be classified into one of the following categories:

- (1) Group A: *MYC* translocation+ by FISH,
- (2) Group B: *MYC* expression in  $\geq 40\%$  of tumor cells by IHC and/or *MYC* gene copy number gain by FISH, or
- (3) Group C: *MYC* translocation by FISH, and *MYC* expression in  $< 40\%$  of tumor cells, and no *MYC* gene copy number gain by FISH.

Subjects will be assigned to Groups A, B, or C according to their *MYC* status as described above. Subjects who are both *MYC* translocation+ by FISH and have *MYC* expression in  $\geq 40\%$  of tumor cells by IHC and/or *MYC* gene copy number gain by FISH will be classified as *MYC* translocation+ and assigned to Group A. Enrollment may continue until the minimum number of subjects are enrolled in Groups A and B.

Subjects in all groups will continue to receive treatment until they meet criteria for treatment discontinuation.

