### **10.5. Study Drug Administration**

#### **10.5.1. CUDC-907**

Subjects will receive CUDC-907 60 mg in 21-day cycles.

CUDC-907 will be administered orally at the assigned dose level and schedule, 60 mg on a 5/2 schedule.

All doses of study drug (in clinic and self-administered) will be administered with meals ( $\pm$  30 minutes) at approximately the same time each dosing day, if possible.

Dose and/or schedule intensity of CUDC-907 may be reduced per protocol due to toxicity.

In the absence of significant toxicity, each subject is expected to complete at least 1 cycle (21 days) of study treatment. However, subjects may continue to receive additional 21-day cycles of CUDC-907 treatment until disease progression has been documented or other discontinuation criteria have been met (Section 9.3.1).

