### 10.5.3.2. CUDC-907 Dose Reductions

**Table 1: Dose Reduction Steps for CUDC-907**

Reduction Steps:	Schedule	Dose
Starting dose	5/2	60 mg
Dose Reductions	Schedule	Dose
First dose reduction	4/3	60 mg
Second dose reduction	5/2	30 mg
Final dose reduction	4/3	30 mg

4/3 = 4 days on/3 days off; 5/2 = 5 days on/2 days off

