### 10.5.3.3. Dose Adjustments for CUDC-907 Hematologic and Non-hematologic Toxicity

The administration of HDAC and PI3K inhibitors has been associated with predictable bone marrow suppression that is typically transient and reversible.

The administration of HDAC and PI3K inhibitors has also been associated with hyperglycemia. This hyperglycemia does not generally result in severe metabolic complications and typically resolves with therapeutic intervention. The treatment goal for glycemic control is fasting plasma glucose  $<$  160 mg/dL; while making every attempt to avoid hypoglycemia. Dose modifications of CUDC-907 are based on the severity of toxicities.

CUDC-907 dose adjustments for hematologic and non-hematologic toxicities are shown in [Table 2](#).

Table 2: CUDC-907 Dose Adjustments for Hematologic and Non-Hematologic Toxicities			
Thrombocytopenia	Grade 1 or 2 No change in dose	Grade 3 or 4 (platelets < 50,000/μL) Hold treatment until platelets ≥ 50,000/μL or baseline, then reduce dose to the next lower dose level (as applicable per Table 1 ).	Grade 4 thrombocytopenia requiring platelet transfusion Hold treatment until platelets ≥ 75,000/μL or baseline, then dose reduce to the next lower dose level (as applicable per Table 1 ).
Neutropenia	Grade 1 or 2 No change in dose	Grade 3 or 4 (ANC < 1,000/uL) Hold treatment until ANC ≥ 1000/μL, then reduce dose to the next lower dose level (as applicable per Table 1 ).	Grade 4 febrile (≥ 38.5° C) neutropenia Hold treatment until febrile neutropenia resolves and ANC ≥ 1000/μL or baseline, then dose reduce to the next lower dose level (as applicable per Table 1 ).
Anemia	Grade 1 or 2 No change in dose	Grade 3 or 4 (hemoglobin < 8 g/dL) Hold treatment until hemoglobin ≥ 10 g/dL or baseline then reduce dose to the next lower dose level (as applicable per Table 1 ).	Grade 4 anemia requiring transfusion Hold treatment until hemoglobin ≥ 10 g/dL or baseline, then dose reduce to the next lower dose level (as applicable per Table 1 ).
Recurrence of Grade 3 or 4 hematologic toxicity will be cause for a second dose modification. If the starting dose does not permit dose modification, then study drug will be discontinued.			

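### Table 2's discontinuation sentence depends on a starting dose that can always be reduced, so it applies to nobody, and the hyperglycemia instructions conflict across Section 8.3.1, Section 10.5.3.1 and Table 2

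*Combined protocol and SAP*

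**What the plan says.** Section 8.1 gives one regimen to all three groups ("All eligible subjects will receive the following treatment"), and Section 10.5.1 fixes it: "CUDC-907 will be administered orally at the assigned dose level and schedule, 60 mg on a 5/2 schedule". Table 1 (Section 10.5.3.2) lists three steps below that dose, from "First dose reduction" to "Final dose reduction".

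Table 2 (Section 10.5.3.3) sets the dose adjustments. In the hematologic part, "Recurrence of Grade 3 or 4 hematologic toxicity will be cause for a second dose modification", followed by "If the starting dose does not permit dose modification, then study drug will be discontinued". The hyperglycemia part repeats that second sentence. It then adds a separate stop for recurrent Grade 3 or 4 events that do not recover within 3 weeks after the second modification, subject to a clinical-benefit exception. The row for other non-hematologic events also ties inability to reduce to the starting dose.

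The hyperglycemia row has three columns:

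- Left: Grade 1 or 2, or asymptomatic Grade 3. The dose is unchanged.
- Middle: symptomatic Grade 3, or Grade 4 with no symptom qualifier. Hold until glucose is under 250 mg/dL and the subject is asymptomatic, and reduce.
- Right: "≥ Grade 3 hyperglycemia not improving despite appropriate treatment for 1 week or symptomatic Grade 4 hyperglycemia". The end of the hold is the same, but the reduction is due "upon return to ≤ Grade 1 or baseline".

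Two other places bear on this. Section 10.5.3.1 treats non-hematologic events of Grade 3 or higher as DLT-like, with limited exclusions, and answers them with discontinuation or reduction. Section 8.3.1 makes discontinuation mandatory for a Grade 4 DLT-like event.

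**The concern.** A stopping sentence that refers to the starting dose makes sense only if subjects can start at different levels, some of them with nothing below. Here they cannot. The situation the sentence seems meant for, a subject with no step left, depends on the current dose, which the sentence does not mention.

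For hyperglycemia, one glucose value can bring in two or three instructions that do not agree.

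At stake are subject safety and the consistency of the exposure data. Dose reductions and discontinuations due to toxicity are among the items the Safety Review Committee weighs under Section 9.3.2, and the Synopsis allows up to 65 sites. If sites settle the same event differently, those counts partly reflect how each site read the table. In the first-in-human study (Section 6.3.1), thrombocytopenia and neutropenia were the named Grade 3 or 4 hematologic events, and the dose-limiting toxicities consisted of diarrhea and hyperglycemia.

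**Working it through.** The plan states no figure to reproduce. The check is a count of dose steps and a side-by-side reading.

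**1. Can the starting-dose condition be true?** Planned weekly dose = dosing days × dose, from Table 1:

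| Table 1 step | Weekly dose | Steps left below |
|---|---|---|
| Start, 60 mg 5/2 | 5 × 60 = 300 mg | 3 |
| First, 60 mg 4/3 | 4 × 60 = 240 mg | 2 |
| Second, 30 mg 5/2 | 5 × 30 = 150 mg | 1 |
| Final, 30 mg 4/3 | 4 × 30 = 120 mg | 0 |

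All subjects start on the first line, with three reductions available. The number who can meet the condition is 0. The only line with no step below is the last, and nobody starts there.

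**2. Hematologic test case.** Take a subject on 30 mg 4/3 with recurrent Grade 3 thrombocytopenia that resolves in 5 days without significant bleeding.

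- Table 2 says to hold, then go to the next lower level as applicable. There is none.
- The discontinuation sentence does not apply (step 1).
- The event is not DLT-like under Section 10.5.3.1. It is not Grade 4 for 7 days or more, there is no significant bleeding, and the delay is under 7 days.
- The hold is under the 4-week limit in Section 10.5.3.1.
- Section 9.3.1 refers unmanageable toxicity to Section 10.5.2, whose platelet criterion is met again at 50,000/μL.

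Only general judgement is left (unacceptable toxicity, which is not defined, or a physician decision). The text does not say whether the subject continues at the same step or stops.

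**3. Hyperglycemia, rule against rule.** This assumes that the event counts as an adverse event under Section 12.1 and is not excluded as clearly due to disease or extraneous factors.

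| State | Table 2 | Section 10.5.3.1 | Section 8.3.1 |
|---|---|---|---|
| Grade 3, asymptomatic, improving within 1 week | No change | Discontinue or reduce | Silent |
| Grade 3, symptomatic | Hold and reduce | Discontinue or reduce | Silent |
| Grade 4, asymptomatic | Hold and reduce (middle column) | Discontinue or reduce | Discontinue |
| Grade 4, symptomatic | Hold and reduce (middle and right columns, different timing) | Discontinue or reduce | Discontinue |

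The first, third and fourth rows conflict. In the first row there is a further problem: the recurrence rule asks for a second modification after any recurrent Grade 3, although the first episode led to none.

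**4. Timing after symptomatic Grade 4.** Table 2 places Grade 3 above 250 mg/dL. A value just under 250 is therefore below Grade 3 but need not be Grade 1. In the right-hand column the hold can thus end before the reduction is due. The retreatment criteria in Section 10.5.2 contain no glucose criterion, so they do not settle which point governs.

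**The case against.** The strongest reply is that the protocol does not leave these subjects without a stop. For hyperglycemia this is correct. A reader might infer from the starting-dose sentence that no discontinuation rule works for hyperglycemia, but the documents do not support that. The 3-week non-recovery rule is in the same row, Section 10.5.3.1 adds the DLT-like and 4-week-hold rules, and Section 8.3.1 adds the Grade 4 rule. At the last step, discontinue or reduce leaves only discontinuation. In the other non-hematologic row, recurrence of Grade 3 is grounds for stopping by itself, so the starting-dose wording matters less there.

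A reader might also infer that symptomatic Grade 4 can restart at either 300 or 240 mg per week. The text does not support that either. Both columns require a reduction, and Section 10.5.3.1 allows full-dose resumption only when no Table 2 criterion is met. What is unclear is when the reduced dose starts.

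The column overlap can be defended as the table's convention: the thrombocytopenia and anemia rows also list a general group and then a more specific one, and the specific column would govern. Likewise, a second modification may simply presume a first. These readings are reasonable, but they do not resolve the timing inside the right-hand cell or the case where no first modification occurred.

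On importance, the first-in-human dose-limiting toxicities arose on other schedules, and Section 6.1.3 reports none at 60 mg 5/2. Medical Monitor agreement is required for DLT-like events and, beyond Cycle 1, for restarts after holds of more than 7 days, which limits variation between sites. The test case in step 2 of the working falls outside both of those requirements.

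**Conclusion.** The point holds in a limited form. The starting-dose sentence is inoperative as written: it can apply to 0 subjects. The practical gap is narrow and mainly hematologic, namely a short, uncomplicated recurrent Grade 3 or 4 cytopenia in a subject already on the last Table 1 step. For hyperglycemia the fault is several rules that disagree, most plainly for Grade 4, where three places give three different instructions. Asymptomatic Grade 3 and the restart timing after symptomatic Grade 4 are lesser inconsistencies.

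The documents do not allow an estimate of how many subjects would reach these situations. The conclusion rests on the single starting dose in Sections 8.1 and 10.5.1, on Table 1 being the full list of steps, and on Grade 3 or 4 hyperglycemia usually qualifying as DLT-like. Neither the sample size nor the interim rule is affected. The sponsor should correct the text because it governs dosing after toxicity.

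**What to change.** Reconcile Section 8.3.1, Section 10.5.3.1, Table 1 and all parts of Table 2 so that:

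- the starting-dose condition, wherever it appears, agrees with the Table 1 steps, and the table says what follows when no lower step exists;
- each hyperglycemia grade and symptom state has one instruction, consistent with the DLT-like rules and with the recurrence sentence;
- the points at which dosing restarts and the reduction takes effect are each stated once.

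Which clinical rule, threshold or stopping condition applies is for the sponsor to decide. The cost is text edits, almost all within Section 10.5.3, with Section 8.3.1 brought into line. This takes an amendment with the ethics review that Section 15.4 requires, and no new assessments.

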## 10.6. Concomitant Medications

Information on concomitant medications will be collected from 30 days prior to study drug dosing through the EOT visit. Information on subsequent anticancer treatments will be collected through the Follow-up visits.

### 10.6.1. Permitted Medications

Antidiarrheal treatment (e.g., loperamide) should be administered immediately upon the first onset of symptoms. Each subject should be instructed to have loperamide or a comparable anti-diarrheal medication (per institutional standard) readily available and to begin treatment for diarrhea at the first episode of poorly formed or loose stools or the earliest onset of bowel movements more frequent than normally expected for the subject until diarrhea free. Subjects will be instructed to notify the Investigator if diarrhea occurs and will be evaluated in the clinic for significant dehydration, possible electrolyte imbalance, and/or ongoing losses. If clinically significant dehydration is present, rehydration and electrolyte repletion per institutional standard will be required. Additionally, subjects will be monitored following rehydration for the risk of recurrence and electrolyte imbalances and also advised regarding appropriate fluid management to reduce the likelihood of subsequent dehydration events.

Antiemetics may be given prophylactically after the first episode of nausea or vomiting per standard of care at each study center.

Unless otherwise prohibited (See Section 10.6.2), supportive therapy for optimal medical care may be administered per institutional standard of care at the study centers.

Growth factor support is permitted for neutropenia or neutropenic fever.

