**Inclusion and Exclusion Criteria (Continued):**

Exclusion Criteria:

1. Known primary mediastinal, ocular, epidural, testicular or breast DLBCL.
2. Patients must not have active CNS involvement of their malignancy. Patients with prior brain metastases are permitted, but must have completed treatment and have no evidence of active CNS disease (clear cerebrospinal fluid [CSF]) for at least 4 weeks prior to the first dose of CUDC-907. Intrathecal chemoprophylaxis to prevent the emergence or recurrence of lymphoma in the CNS is permitted on study and may be administered per institutional guidelines.
3. Known allergy or hypersensitivity to phosphatidylinositol 3-kinase (PI3K) inhibitors or any component of the formulations used in this study.
4. Cytotoxic anticancer therapy (e.g., alkylating agents, anti-metabolites, purine analogues) within 2 weeks of study entry.
5. Radiotherapy delivered to non-target lesions within one week prior to starting study treatment or delivered to target lesions that will be followed on the study (**NOTE:** prior sites of radiation will be recorded).
6. Treatment with experimental therapy within 5 terminal half-lives ( $t_{1/2}$ ) or 4 weeks prior to enrollment, whichever is longer.
7. Current or planned glucocorticoid therapy, with the following exceptions:
  - Doses  $\leq 1$  mg/kg/day prednisolone or equivalent glucocorticoid and inhalational therapies for conditions such as mild chronic obstructive pulmonary disease (COPD) and asthma are allowed.
  - Replacement dosing of steroids (defined as  $< 30$  mg/day hydrocortisone or the equivalent) is allowed, provided that the steroid dose has been stable or tapering for at least 14 days prior to the first dose of CUDC-907.
8. Graft versus host disease following transplant within 100 days prior to study treatment.
9. Major surgery, other than diagnostic surgery, occurring 4 weeks prior to study treatment.
10. Diabetes mellitus that is not controlled with medication.
11. Serious infection requiring intravenous antibiotic therapy within 14 days prior to study treatment.

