### **8.4. Planned Duration of Treatment**

CUDC-907 will be taken until disease progression, withdrawal from study, unacceptable toxicity, pregnancy, initiation of another anticancer or experimental therapy, noncompliance with study procedures, or study discontinuation.

Dose and/or schedule intensity of CUDC-907 may be reduced due to toxicity.

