## 9.2. Patient Exclusion Criteria:

1. Known primary mediastinal, ocular, epidural, testicular or breast DLBCL.
2. Patients must not have active CNS involvement of their malignancy. Patients with prior brain metastases are permitted, but must have completed treatment and have no evidence of active CNS disease (clear cerebrospinal fluid [CSF]) for at least 4 weeks prior to the first dose of CUDC-907. Intrathecal chemoprophylaxis to prevent the emergence or recurrence of lymphoma in the CNS is permitted on study and may be administered per institutional guidelines.
3. Known allergy or hypersensitivity to PI3K inhibitors or any component of the formulations used in this study.
4. Cytotoxic anticancer therapy (e.g., alkylating agents, anti-metabolites, purine analogues) within 2 weeks of study entry.
5. Radiotherapy delivered to non-target lesions within one week prior to starting study treatment or delivered to target lesions that will be followed on the study (note: prior sites of radiation will be recorded).

6. Treatment with experimental therapy within 5 terminal half-lives ( $t_{1/2}$ ) or 4 weeks prior to enrollment, whichever is longer.
7. Current or planned glucocorticoid therapy, with the following exceptions:
  - Doses  $\leq 1$  mg/kg/day prednisolone or equivalent glucocorticoid and inhalational therapies for mild chronic obstructive pulmonary disease (COPD) or asthma are allowed.
  - Replacement dosing of steroids (defined as  $< 30$  mg/day hydrocortisone or the equivalent) is allowed, provided that the steroid dose has been stable or tapering for at least 14 days prior to the first dose of CUDC-907.
8. Graft versus host disease following transplant within 100 days prior to study treatment.
9. Major surgery, other than diagnostic surgery, occurring 4 weeks prior to study treatment.
10. Diabetes mellitus that is not controlled with medication.
11. Serious infection requiring intravenous antibiotic therapy within 14 days prior to study treatment.

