### 10.6.2. Drug Interactions/Precautions

*In vitro*, CUDC-907 competitively inhibits cytochrome P450 isoenzymes CYP2C9, CYP2C19, CYP2D6 and CYP3A4 with half maximal inhibitory concentration ( $IC_{50}$ ) values of > 10, > 10, > 10, and 0.28 to 13.58  $\mu$ M, respectively. Currently, it is not known whether achievable plasma exposures of CUDC-907 in humans will approach these *in vitro* determined values. These data suggest that CUDC-907 may inhibit cytochrome P450 isoenzymes CYP2C9, CYP2C19, CYP2D6, and CYP3A4, although the clinical significance of this potential interaction has not been investigated. Subjects receiving concomitant medications metabolized by these enzymes should be monitored at the discretion of the Investigator.

Please refer to the CUDC-907 Investigator's Brochure for additional drug interaction information.

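### Glucocorticoids are limited only at entry, and the 14-day stability condition skips the larger permitted dose, so a steroid started or raised between scans could count towards ORR

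*Combined protocol and SAP*

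**What the plan says.** **At entry.** Exclusion 7 (synopsis and Section 9.2) bars "Current or planned glucocorticoid therapy, with the following exceptions". There are two exceptions.

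- The larger one is a dose of up to 1 "mg/kg/day prednisolone or equivalent glucocorticoid and inhalational therapies for mild chronic obstructive pulmonary disease (COPD) or asthma are allowed" in Section 9.2. The synopsis words the end of it differently: "inhalational therapies for conditions such as mild chronic obstructive pulmonary disease (COPD) and asthma are allowed". Neither version asks for a stable dose.
- The smaller one is replacement dosing below 30 mg/day hydrocortisone or equivalent. Only this one carries a condition: "provided that the steroid dose has been stable or tapering for at least 14 days prior to the first dose of CUDC-907".

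**During treatment.** Section 10.6.1 states: "Unless otherwise prohibited (See Section 10.6.2), supportive therapy for optimal medical care may be administered per institutional standard of care". It adds: "Antiemetics may be given prophylactically after the first episode of nausea or vomiting per standard of care at each study center". Section 10.6.2, the place named for prohibitions, deals with cytochrome P450 and instructs: "Subjects receiving concomitant medications metabolized by these enzymes should be monitored at the discretion of the Investigator". Beyond that it refers to the Investigator's Brochure. It neither prohibits a drug nor mentions steroids. The nearest on-treatment limit is in Section 8.4, which ends study drug on "initiation of another anticancer or experimental therapy".

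**In the analysis.** Sections 14.4.3 and 14.4.8 contain no rule for a response that follows steroid use.

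**The concern.** ORR here is a change from baseline with no control group, so shrinkage caused by a steroid cannot be told apart from shrinkage caused by CUDC-907. Section 6.1.1.1 itself lists prednisone and dexamethasone as components of DLBCL regimens. Occasions for a steroid are foreseeable. Nausea was among the commonest drug-related events in Phase 1, though low grade (Section 6.3.1), and the stopping guidelines in Section 9.3.2 name colitis and pneumonitis.

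The analysis sets do not remove the problem. Permitted use is not a deviation, so such a subject stays in the primary ITT analysis and, if otherwise eligible, in the Evaluable Population. Central reviewers are blinded to the investigator's reading, but a scan does not show why a node shrank. The interim decision uses the local reading and turns on a single count, and a group that passes goes on from 25 evaluable subjects towards 50.

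**Working it through.** **1. Which rule applies when**

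| Period | Rule for systemic glucocorticoids | Left open |
|---|---|---|
| At entry | Exclusion 7: none current or planned, beyond the two exceptions | Doses within the 1 mg/kg/day exception need not be stable |
| Baseline CT to first dose | 14-day stable-or-tapering condition, replacement dosing only | A start or rise within the 1 mg/kg/day exception |
| On treatment | 10.6.1 permits unless 10.6.2 prohibits; 10.6.2 prohibits nothing | Any unplanned supportive start or increase |

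**2. Time between scans**

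- The baseline CT may be as early as Day -28 (Section 13.1). With no Day 0, that is 28 days before Day 1.
- The first response CT falls on Cycle 2 Day 15-21, ± 3 days (Section 11.3.2). With 21-day cycles this is study Day 36-42, widened to Day 33-45, or 32 to 44 days after Day 1.
- The longest separation is therefore 28 + 32 = 60 to 28 + 44 = 72 days. At most 28 of these belong to the entry gap; the other 32 to 44 belong to the on-treatment gap.

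**3. The plan's own figures**

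Exact binomial limits reproduce the figures needed here.

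- Interim, one-sided 95% lower bound: 5/25 gives 8.2% (stop) and 6/25 gives 11.0% (continue).
- Final, two-sided 95%: 15/50 gives 17.9% to 44.6%, a width of 44.6 - 17.9 = 26.7 points.

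**4. Effect at the interim**

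Let p be the ORR from the drug alone and s the added proportion of subjects who respond only because of a steroid. Both are assumed, since the documents give neither. Then X ~ Binomial(25, p + s), and the group continues if X ≥ 6. For scale, s = 1 point would arise if 10% of subjects newly took steroids and 10% of those responded to the steroid alone (0.10 × 0.10 = 0.01). An s of 4 points is an average of one such response per 25 subjects.

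| Drug-only ORR | s = 0 | 0.5 points | 1 point | 2 points | 4 points |
|---|---|---|---|---|---|
| 10% | 3.3% | 4.1% | 5.0% | 7.1% | 12.7% |
| 15% | 16.2% | 18.0% | 20.0% | 24.2% | 33.5% |
| 20% | 38.3% | 40.8% | 43.2% | 48.2% | 57.7% |

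At 1 point the chance of continuing rises by 1.7, 3.8 and 4.9 percentage points in the three rows. At 4 points it rises by 9.4, 17.3 and 19.4.

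**5. Effect at the final analysis**

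One response is 1/50 = 2 points of ORR. Going from 12/50 to 13/50 moves the lower limit from 13.1% to 14.6%, which is small beside the 26.7-point interval.

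**The case against.** Much is already controlled. Steroids foreseen at entry and above the allowance are excluded. A steroid given as lymphoma treatment can be read as another anticancer therapy, which ends study drug. Antiemetic prophylaxis begins only after a first episode, and the common nausea was Grade 1 or 2. Concomitant medications are recorded from 30 days before dosing and updated at every visit, so affected responders could be found afterwards, and the SAP has yet to be finalised. Subjects have had 2 to 4 prior lines, so earlier steroid exposure may blunt any effect. The final analysis is an estimate with an interval, not a test, and one response hardly moves it.

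These points stand, and they limit the size. They do not close the gap: supportive use for nausea, symptoms or toxicity is not caught by the anticancer rule, and a later SAP can analyse steroid use but cannot limit it.

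Two further points narrow the concern. The 1 mg/kg/day exception can be read as confined to conditions such as mild COPD or asthma. That reduces who qualifies but adds no stability condition. The direction is also not fixed: a steroid started or raised after the baseline CT favours the drug, whereas a baseline dose that falls before the response CT can work against it.

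A reader might infer that steroids will in practice carry a failing group through the interim, or that every group will gain a steroid-driven response. The documents do not support this, because they say nothing about how often sites give systemic steroids or how often these patients respond to them.

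**Conclusion.** Both gaps are in the text: no limit on unplanned systemic glucocorticoids during treatment, and no stability condition on the larger entry exception. As the plan stands, shrinkage due to a steroid can be counted as response. The bias favours the drug when a steroid is started or raised after the baseline CT.

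Its size is unknown and probably small. The interim is the sensitive point, because 5 and 6 responses lead to opposite decisions. The interim figures assume steroid-only responses in 0.5 to 4% of subjects, added to a drug-only ORR of 10 to 20%. A reader might infer that the primary ORR is materially inflated, but at 2 points per response the documents give no ground for that. The change is worth making because it is cheap and because, without a control arm, the bias cannot be separated out later. Confidence is medium.

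**What to change.** 1. **Exclusion 7, synopsis and Section 9.2, in identical wording.** Require every systemic glucocorticoid to be stable or tapering for at least 14 days before the first dose, with no increase after the baseline CT. Word the 1 mg/kg/day exception the same way in both places.
2. **Section 10.6.2.** State that systemic glucocorticoids are not started, or raised above the entry dose, during treatment, except as a short course for an adverse event that has no suitable non-steroid treatment. Non-glucocorticoid antiemetics come first, and dose and dates are recorded.
3. **Section 14.4.3.** Add a sensitivity ORR per group, at the interim and final analyses. Count as a non-responder any subject whose first CR or PR follows a systemic glucocorticoid started or raised at any time between the baseline CT and that response scan, leaving aside single antiemetic doses. List steroid use for all responders. Leave the primary analysis unchanged.

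**Cost.** Protocol wording, one table and one listing, with no new visit or scan, since Sections 10.6 and 11.2.11 already collect concomitant medications. A few subjects may enter later, sites lose some choice of antiemetic, and the sensitivity ORR will be slightly lower because it also discounts some true drug responses. The stable-or-tapering wording still allows a falling dose, which can bias against the drug; the listing should make such cases visible among responders only.
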